1211 1212 1213 1214 1215	The approach to sample size and statistical analyses are summarized below. A detailed statistical analysis plan will be written and finalized prior to the completion of the study. The analysis plan synopsis in this chapter contains the framework of the anticipated final analysis plan.
1213 1216 1217 1218 1219 1220 1221 1222	This phase II clinical trial is conducted to assess the short term effect of combination steroid + anti-VEGF therapy on visual acuity and OCT retinal thickness, in comparison with that of continued anti-VEGF therapy alone, in eyes with persistent central-involved DME and visual acuity impairment despite previous anti-VEGF treatment. The primary outcome of the study will be the mean change in visual acuity at the 24-week post-randomization visit, adjusted for the baseline (randomization) visual acuity.
1222	The treatment groups include the following:
1224	• Group A: Sham + intravitreal ranibizumab 0.3 mg
1225	• Group B: Intravitreal dexamethasone +intravitreal ranibizumab 0.3 mg
1226	
1227	7.1 Sample Size
1228	This phase II study will include 75 study eyes (from approximately 62 participants) in each
1229	treatment group.
1230	
1231	The primary analysis consists of a statistical estimation of the difference in mean change in visual
1232	acuity letter score at the 24-week post-randomization visit, adjusted for the baseline visual acuity
1233 1234	and correlation between eyes, between the sham + ranibizumab group and the combination of corticosteroid+ ranibizumab group.
1234	concosteroid+ ramoizumao group.
1235	7.2 Sample Size Assumptions and Precision Estimates
1230	To estimate the standard deviation (SD) of change in visual acuity from baseline (randomization)
1238	to the 24-week visit (primary outcome visit), data from the DRCR.net Protocol I were reviewed.
1239	Of eyes that completed the 1-year visit, 61 eyes were identified at the 32-week visit to have 1)
1240	OCT CSF≥250 µm, 2) VA between 20/320 to 20/32; and 3) received at least 3 ranibizumab
1241	injections from the 16-week visit to prior to the 32 week-visit. All these eyes had received at least
1242	3 ranibizumab injections prior to the 16-week visit and met the OCT and VA thresholds above,
1243	mimicking the minimum number of injections required for enrollment into the run-in phase of this
1244	protocol. The mean change in visual acuity letter score from the 32-week visit (to mimic
1245	randomization visit of this protocol) to the 52-week visit (to mimic the 24-week visit of this
1246	protocol) for these 61 eyes, adjusted for baseline visual acuity, was +1.9 (95%CI: +0.1 to +3.7).
1247	The standard deviation for the mean change in visual acuity letter score adjusted for correlation
1248	with baseline visual acuity value was 6.9 letter score (95% CI: 5.9 to 8.4).
1249	
1250	The following table shows half-widths of 95%CI on the difference in mean visual acuity change

- between treatment groups for a range of SDs and sample sizes. For the sample size in each group
- 1252 of 70 (increased to 75 for approximately 5% lost to follow-up) that will be used, a two-sided 95%
- 1253 CI for the difference of the two means in visual acuity change from randomization to 24-week visit
- 1254 will extend 2.3 visual acuity letter score in either direction from the observed difference in means,
- assuming that the common standard deviation is a letter score of 7 (~the midpoint for the estimated
- 1256 standard deviation), not adjusting for correlation between eyes in participants with two study eyes.

- 1257 Similarly, half-width of the 95% CI using a standard deviation of 9 (~ the upper confidence limit
- 1258 for the estimated standard deviation) will be a letter score of 3.0. Adjustment in the primary
- 1259 analysis for between-eye correlation is expected to slightly reduce the expected width of the 1260 confidence interval over the tabled values.
- 1260
- Based on the above information, with an alpha of 0.05, if the true visual acuity mean difference is
- 1263 5 letters and the standard deviation is 9 then there is 90% power to detect a difference in visual
- acuity change between treatment groups.
- 1265

Standard Deviation	Sample Size Per Group				
	25	50	70	100	125
6	3.3	2.4	2.0	1.7	1.5
7	3.9	2.7	2.3	1.9	1.7
8	4.4	3.1	2.7	2.2	2.0
9	5.0	3.5	3.0	2.5	2.2
10	5.5	3.9	3.3	2.8	2.5
11	6.1	4.3	3.6	3.0	2.7

4.0

3.3

3.0

1266 Half-Width of a 95% Confidence Interval for the Difference in Mean visual acuity Change

1267

1268 **7.3 Efficacy Analysis Plan**

12

1269 7.3.1 Primary Outcome Analysis 1270 The primary analysis consists of the estimation of the difference in mean change between the

6.7

treatment groups in visual acuity letter score from randomization to the 24-week postrandomization visit, adjusted for randomization visual acuity and correlation between eyes of participants with two study eyes.

4.7

1274

1275 The estimation of treatment group difference in mean change in visual acuity from randomization 1276 to the 24-week visit will be performed using an analysis of covariance (ANCOVA) model, with the change in visual acuity measurements at 24 weeks fitted as the dependent variable, and the 1277 1278 treatment group as the independent variable, adjusting for the randomization stratification factor, and for the baseline measurement (visual acuity value at randomization visit) by including each as 1279 a covariate in the model. The treatment effect will be reported as the mean difference (and standard 1280 1281 deviation) between treatment groups in change of visual acuity letter score from randomization to 24-week visit with 95%CI from ANCOVA model. The significance level used for the final primary 1282 1283 analysis will be 0.05. The study is not powered to establish treatment efficacy; however, treatment comparison will be conducted for visual acuity and OCT retinal thickness outcomes to assess 1284 1285 treatment effect.

1286

1288

1289

1287 There will be two analyses: an "intent-to-treat" analysis (ITT) and a "per-protocol" analysis:

- The intent-to-treat analysis will include all randomized eyes. Rubin's multiple
 - imputation method will be used to impute missing data at the 24-week visit.

1290 The per-protocol analysis will be performed including only participants who complete all • 1291 required injections without receiving any non-protocol treatments and have data at the 1292 24-week visit. 1293 • The intent-to-treat analysis is considered the primary analysis. If the intent-to-treat and 1294 per-protocol analyses yield the same results, the per-protocol analysis will be used to provide supportive evidence of the magnitude of treatment effect among patients who 1295 received the treatment. If the results of the two methods differ, exploratory analyses will 1296 1297 be performed to evaluate the factors that have contributed to the differences. A sensitivity analysis will be conducted to compare the results from multiple imputation with those 1298 1299 using a per-protocol analysis only including study participants who completed the 24-1300 week visit and with results from last-observation-carried-forward. 1301 1302 Generalized estimating equations (GEE) will be used to adjust for the correlation between eyes 1303 of patients who have two study eyes. 1304 1305 Although expected to be under-powered, pre-planned subgroup analyses will be conducted in the same way as the primary analysis and include stratification by improvement in OCT CSF thickness 1306 during run-in phase visits by $\geq 10\%$ at any visit, and improvement in VA during run-in phase by 5 1307 or more letters at any visit. Other subgroup analyses will be described in the detailed Statistical 1308 1309 Analysis Plan. These subgroup analyses will be used to guide choice of pre-planned subgroup 1310 analyses in the phase III trial. 1311 1312 Imbalances between groups in important covariates are not expected to be of sufficient magnitude 1313 to produce confounding; however, a second analysis that adjusts for imbalanced baseline covariates will be performed. If results are similar to the primary analysis, the primary analysis 1314 will be accepted as the definitive analysis; otherwise, the reasons for the difference will be 1315 1316 explored. 1317 1318 There are no data to suggest that the treatment effect will vary by sex or race and ethnicity. 1319 However, both of these factors will be evaluated in exploratory analyses. 1320 1321 7.4 Secondary Outcomes 1322 In addition to the primary outcome, the following secondary outcomes will be estimated, and their 1323 95% CI will be obtained in each treatment group and compared between treatment groups: 1324 1325 • Percent of eyes with at least 10 and at least 15 letter gain (increase) or loss (decrease) in E-ETDRS letter score visual acuity at 24 weeks 1326 1327 • Visual acuity AUC between randomization and 24 weeks • Mean change in OCT CSF thickness, adjusted for thickness at time or randomization, 1328 1329 using ITT, and per-protocol analyses • Percent of eyes with ≥ 1 and ≥ 2 logOCT step gain or loss in CSF thickness at 24-week 1330 1331 visit • Percent of eyes with OCT CSF thickness (in micros) < the following gender and OCT 1332 machine-specific values at 24-week visit: <290 in women and <305 in men in Zeiss 1333 1334 Cirrus; <305 in women and <320 in men in Heidelberg Spectralis • OCT CSF thickness area under the curve (AUC) between randomization and 24 weeks 1335 • Percent of eyes with worsening or improvement of diabetic retinopathy on clinical exam 1336 1337

1338

1339 7.4.1 Secondary Outcomes Analysis

1340 Analyses of secondary outcomes will be conducted as follows:

1341 Binary outcomes will be analyzed using logistic regression to control for baseline level of the

1342 outcome. Continuous outcome comparisons will be performed using ANCOVA with adjustment

1343 for baseline values. All linear model assumptions will be verified including linearity, normality

- 1344 of residuals, and homoscedasticity. If model assumptions are not met, a nonparametric analogue
- 1345 for ANCOVA will be considered. Multple imputation method will be implemented for missing 1346 data. GEE will be used to adjust for correlation between eyes of participants with two study
- 1347 eyes.
- 1348
- 1349

1350 7.5 Safety Analysis Plan

1351 Adverse events will be categorized as study eye, non-study eye, and systemic. The events will be tabulated and compared between treatment groups. Separate analyses will compare related adverse 1352

- 1353 events between groups.
- 1354
- 1355 Specific adverse events of interest will include:
- 1356 Injected-related: increased intraocular pressure, endophthalmitis, retinal detachment, retinal tears, intraocular hemorrhage 1357
- Ocular drug-related: increased intraocular pressure, need for ocular anti-hypertensives, 1358
- 1359 glaucoma surgery or other IOP-lowering procedures, development or worsening of cataract 1360 and cataract extraction, intraocular hemorrhage, inflammation, migration of Ozurdex to the anterior chamber and subsequent corneal complications 1361

1362 Systemic drug-related: Deaths, participants with at least one hospitialization, participants

with at least one SAE, and cardiovascular events and cerebrovascular events as defined by 1363 Antiplatelet Trialists' Collaboration 1364

1365 1366 • Systemic adverse events for participants with two study eves will be evaluated separately from participants with one study eye.

- 1367
- 1368

1369 Further definitions of the events for analysis and the analytic approach will be provided in the 1370 detailed statistical analysis plan.

1371 1372

1373 7.6 Additional Analysis Objectives Related to Design of Phase III Trial

1374 If the results of this study support proceeding with a phase III trial, information from this study 1375 will 1) be used to estimate recruitment potential; and 2) contribute to designing the phase III trial. The standard deviation of the difference in mean change in visual acuity will be used in the 1376 1377 sample size calculation of the phase III trial. The recruitment potential for a phase III trial will be assessed based on the average monthly enrollment of participants into this study. The sample 1378 1379 size estimate that would be calculated for a phase III trial weighed against recruitment projection 1380 from this phase II trial will aid in the assessment of feasibility of a phase III trial in terms of recruitment.

- 1381
- 1382

1383 Additional outcomes that will be assessed to aid in the design of a phase III trial include: 1) success 1384 of the run-in phase in identifying eyes with "persistent DME" following anti-VEGF therapy (for

- 1386 or criteria for randomization may be adjusted), 2) success of masking via sham injections and 3)
- 1387 duration of steroid effect.
- 1388

1389 7.7 Additional Tabulations and Analyses

- 1390 The following will be tabulated according to treatment group:
- 1391 1) Baseline demographic and clinical characteristics (subject and ocular-level data)
- 1392 2) Visit completion rate for each visit
- 13933) Protocol deviations
- 1394

1395 **7.8 Interim Monitoring Plan**

- 1396 Formal interim efficacy analyses are not planned. However, at approximately 6-month intervals
- the DSMC will review a compiled ocular and systemic adverse event data report as well as visual
- acuity by treatment group.
- 1399
- 1400 A minimal amount of alpha spending (0.0001) will be allocated for each DSMC review of the
- 1401 data and depending on the actual number of reviews, the final overall type 1 error at the end of
- 1402 the trial will be adjusted accordingly.

1403		Chapter 8. REFERENCES
1404 1405	1.	Centers for Disease Control and Prevention. State-specific incidence of diabetes among
1406		adultsparticipating states, 1995-1997 and 2005-2007. MMWR Morb Mortal Wkly Rep.
1407		Oct 31 2008;57(43):1169-1173.
1408	2.	Shaw JE, Sicree RA, Zimmet PZ. Global estimates of the prevalence of diabetes for 2010
1409	-	and 2030. Diabetes Res Clin Pract. Jan 2010;87(1):4-14.
1410	3.	Kempen JH, O'Colmain BJ, Leske MC, et al. The prevalence of diabetic retinopathy

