d=does not need to be repeated if HbA1c is available from within the prior 3 months. If not available, can be performed within 3 weeks after randomization.

429 **1.4 General Considerations**

The study is being conducted in compliance with the policies described in the DRCR.net Policies
document, with the ethical principles that have their origin in the Declaration of Helsinki, with
the protocol described herein, and with the standards of Good Clinical Practice.

- 434 The DRCR.net Procedures Manuals (Visual Acuity-Refraction Testing Procedures Manual, OCT
- 435 Manuals, and Study Procedures Manual) provide details of the examination procedures and
- 436 intravitreal injection procedure.
- 437
- 438 Data will be directly collected in electronic case report forms, which will be considered the 439 source data.
- 440

441 The participant will be masked to the treatment group assignment. Visual acuity testers

- 442 (including refractionists) and OCT technicians will be masked to treatment group at the primary
- 443 outcome visit (24 weeks). Investigators will not be masked to treatment group assignment.
- 444
- There is no restriction on the number of study participants to be enrolled by a site.
- 446
- 447 A risk-based monitoring approach will be followed, consistent with the FDA "Guidance for

448 Industry Oversight of Clinical Investigations — A Risk-Based Approach to Monitoring" (August

- 449 2013).
- 450
- 451 The risk level is considered to be research involving greater than minimal risk.

452	
453 454	Chapter 2. STUDY PARTICIPANT ELIGIBILITY AND ENROLLMENT
454	STUDI FARTICIFANT ELIGIDILITT AND ENROLLMENT
456	2.1 Identifying Eligible Study Participants and Obtaining Informed Consent
457	A minimum of 150 eyes are expected to be enrolled into the randomization phase. Assuming that
458	20% of the study participants have two study eyes, this equates with an enrollment of about 125
459	study participants, with a goal to enroll an appropriate representation of minorities. As the
460	enrollment goal approaches, sites will be notified of the end date for recruitment. Study
461	participants who have signed an informed consent form or are in the run-in phase can be
462	randomized up until the end date, which means the recruitment goal might be exceeded.
463	1 7 8 8
464	Potential eligibility will be assessed as part of a routine-care examination. Prior to completing

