814 The treatment groups are as follows: 815 Group A: Sham + intravitreal ranibizumab 0.3 mg • Group B: Intravitreal dexamethasone +intravitreal ranibizumab 0.3 mg 816 • For both treatment groups, the initial ranibizumab injection must be given on the day of 817 818 randomization. The sham or dexamethasone injection will be given within 0-8 days of the 819 ranibizumab injection. If the injections are given consecutively on the same day, the sham 820 injection must be given first in Group A and the ranibizumab injection must be given first in 821 Group B. 822 823 Focal/grid laser is not permitted in the study eye. 824 825 4.6 Follow-Up Study Visits During the Randomization Phase The schedule of protocol-specified follow-up visits post-randomization is as follows: 826 827 828 • 4 weeks (± 1 week) 829 • 8 weeks (± 1 week) 830 • 12 weeks (± 1 week) 831 • 16 weeks (± 1 week) 832 • 20 weeks (± 1 week) 833 • 24 weeks (±1 week)– primary outcome visit 834 835 A minimum of 21 days is required between injections. An additional visit may be required for 836 completion of the second (steroid/sham) injection at randomization and 12 weeks. 837 838 4.7 Follow-Up Testing Procedures During the Randomization Phase 839 The following procedures will be performed at each protocol visit unless otherwise specified. A 840 grid in section 1.3 (J) summarizes the testing performed at each visit. 841 842 Visual acuity testers (including refractionist) and OCT technicians will be masked to treatment 843 group at the primary outcome visit (24 weeks). 844 845 1. Best-corrected E- ETDRS visual acuity testing in each eye A protocol refraction in the study eye is required at all protocol visits. Protocol refraction 846 • 847 in the non-study eye at the 24 week-visit only. When a refraction is not performed, the 848 most-recently performed refraction is used for the testing. 849 2. OCT on the study eye 850 3. Ocular exam on the study eye, including slit lamp examination, lens assessment, 851 measurement of intraocular pressure and dilated ophthalmoscopy 852 853 All of the testing procedures do not need to be performed on the same day, provided that they are 854 completed within the time window of a visit and prior to initiating any retreatment. 855 856 Testing procedures at unscheduled visits are at investigator discretion. However, it is 857 recommended that procedures that are performed should follow the standard DRCR.net protocol 858 for each procedure. If the study participant returns following a protocol visit specifically to 859 receive a study injection, testing prior to the injection is at investigator discretion. 860

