 - 995
 - 996 Study participants who withdraw will be asked to have a final closeout visit at which the testing
 - 997 described for the protocol visits will be performed. Study participants who have an adverse effect
 - attributable to a study treatment or procedure will be asked to continue in follow-up until the
 - 999 adverse event has resolved or stabilized.
 - 1000
 - 1001 Study participants who withdraw or are determined to have been ineligible post-randomization
 - 1002 will not be replaced.
 - 1003

1004 **5.8 Discontinuation of Study**

- 1005 The study may be discontinued by the Executive Committee (with approval of the Data and
- Safety Monitoring Committee) prior to the preplanned completion of follow-up for all studyparticipants.
- 1008

1009 **5.9 Contact Information Provided to the Coordinating Center**

- 1010 The Coordinating Center will be provided with contact information for each study participant.
- 1011 Permission to obtain such information will be included in the Informed Consent Form. The contact
- 1012 information may be maintained in a secure database and will be maintained separately from the
- 1013 study data.
- 1014
- 1015 Phone contact from the Coordinating Center will be made with each study participant in the first
- 1016 month after randomization and prior to the 24-week visit. Additional phone contacts from the
- 1017 Coordinating Center will be made if necessary to facilitate the scheduling of the study participant
- 1018 for follow-up visits. A participant-oriented newsletter and/or study logo item may be sent during
- 1019 the study.
- 1020
- 1021 Study participants will be provided with a summary of the study results in a newsletter format 1022 after completion of the study by all participants.
- 1023

1024 5.10 Study Participant Reimbursement

- 1025 The study will be providing the study participant with a \$25 gift card per completed protocol
- 1026 visit. Additional travel expenses will be paid in select cases for participants with higher
- 1027 expenses.

1028 1029	Chapter 6. ADVERSE EVENTS
1030	
1031	6.1 Definition
1032	An adverse event is any untoward medical occurrence in a study participant, irrespective of
1033	whether or not the event is considered treatment-related.
1034	
1035	6.2 Recording of Adverse Events
1036	Throughout the course of the study, all efforts will be made to remain alert to possible adverse

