 - Footnote No. of missing values and No. of values truncated at 3 standard deviation from the mean (if any)¹
 - Review lens status for eyes improved or worsened on visual acuity at 24 weeks [Discussion text]
 - iii. Area under the curve (AUC) between randomization and 24 weeks using truncated data [Figure 2]
 - Mean \pm SD
 - Median [IQR]
 - Note: AUC is computed only for those completing the 24 week follow-up visit.
 - b. Compare change in visual acuity at 24 weeks from randomization between treatment groups
 - Perform Markov Chain Monte Carlo multiple imputation² on missing data (100 imputations) for change in visual acuity at 24 weeks using all available visual acuity data at post randomization follow-up visits, accounting for treatment group assignment, randomization visual acuity value, laterality and improvement in visual acuity during run-in phase. Create flags for binary outcomes specified above based on imputed data.

- ii. Primary analysis: Perform a linear mixed effects model for treatment group comparison of mean change in visual acuity at 24 weeks from randomization. (%*MIAnalyzeMeanMixed* macro)
 - Truncated change in visual acuity letter scores at 24 weeks will be fitted as the dependent variable, and the treatment group as the independent variable, adjusting for randomization visual acuity value, randomization stratification factors (laterality and improvement in visual acuity during run-in phase as defined in the protocol) by including each as a fixed effect in the model. A random subject effect will be included to adjust for the correlation between eyes of participants who have two randomized eyes (assuming a compound symmetry covariance structure).
 - Run the model on observed data to check model assumptions including residual analysis, goodness of fit and influence diagnostics [**not in text**]
 - Run the model on the imputed datasets and report the adjusted mean difference, 95% confidence interval, and *P*-value from treatment group comparison [**Table 2**]
 - Assessment of confounding: Impute the outcome accounting for additional pre-specified potential confounding factors, including age, duration of diabetes, HbA1c levels, retinal thickening on OCT, and diabetic retinopathy severity on clinical exam. All categorical covariates with more than 2 levels are collapsed to a binary covariate for modeling to aid convergence. Mimic primary analysis and obtain *P*-value for treatment group comparison.

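### A participant who withdraws is not asked for the 24-week test, so the primary value is imputed from measurements that need not be masked; the effect is small and the remedy cheap

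*Protocol*

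**What the plan says.** - **Withdrawal (protocol 5.7).** "Study participants who withdraw will be asked to have a final closeout visit at which the testing" of the protocol visits is performed. No week is given for this visit, and nothing asks the participant to come back at 24 weeks. Continued follow-up is requested only of participants with an adverse effect "attributable to a study treatment or procedure will be asked to continue in follow-up until the" event resolves or stabilizes.
- **Masking (protocol 1.4 and 4.7).** Of the acuity testers, section 1.4 says "including refractionists) and OCT technicians will be masked to treatment group at the primary" outcome visit, and section 4.7 repeats the limit to 24 weeks. No masking rule covers testers at weeks 4 to 20 or at closeout. Section 1.4 also states "The participant will be masked to the treatment group assignment" and "Investigators will not be masked to treatment group assignment".
- **Primary analysis (protocol 7.3.1).** "The intent-to-treat analysis will include all randomized eyes", with multiple imputation where the 24-week value is missing. A last-observation-carried-forward (LOCF) comparison is named as a sensitivity analysis.
- **Imputation (SAP item 4.b.i).** The 24-week acuity change is imputed "using all available visual acuity data at post randomization follow-up visits", accounting for treatment group, randomization acuity, laterality and run-in acuity improvement. The item does not restrict the input to masked measurements and does not mention the closeout visit.

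**The concern.** The protocol treats tester and refractionist conduct as a risk worth controlling, because it requires masking at the visit that supplies the primary outcome. An eye whose participant leaves early loses that protection. Its 24-week value is replaced by an imputation built on measurements taken by staff who are allowed to know the arm. Some people who will not continue with monthly visits or injections might still accept a single acuity and OCT test at 24 weeks, and section 5.7 never asks them. At stake are a few masked, on-time primary values, and some exposure of the imputed values to measurement bias that differs by arm. Participants with two study eyes have one eye in each arm, so one such withdrawal removes an observed value from both.

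**Working it through.** **1. The plan's own yardstick (protocol 7.2).** Inputs: 70 analysable eyes per group, SD 7.

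Half-width = 1.96 × SD × √(2/n) = 1.96 × 7 × √(2/70) = 2.32 letters. The plan states 2.3. With SD 9 the result is 2.98, and the plan states 3.0. Both reproduce.

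**2. How many eyes are affected.** Section 7.2 raises 70 to 75 per group for about 5% loss to follow-up.
- 70 / (1 − 0.05) = 73.7, so 74; the plan uses 75.
- 0.05 × 75 = 3.75, so about 4 eyes per group lack a 24-week value.
- This is an upper figure for withdrawals, because it also includes participants who cannot be contacted.

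**3. How far the treatment difference could move.** The documents give no tester-bias figure, so these are assumptions: a between-arm bias of 2 to 10 letters in the earlier measurement, and a weight of 0.5 to 1 for that measurement in the imputed value. A weight of 1 corresponds to LOCF.

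Shift = share imputed × bias × weight

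| Share missing | Eyes per group (of 75) | Bias 2, weight 0.5 | Bias 5, weight 1 | Bias 10, weight 1 |
|---|---|---|---|---|
| 5% (planned) | 3.75 | 0.05 | 0.25 | 0.5 |
| 10% | 7.5 | 0.1 | 0.5 | 1.0 |
| 15% | 11.25 | 0.15 | 0.75 | 1.5 |

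At the planned loss, 0.05 / 2.3 = 2% and 0.5 / 2.3 = 22% of the half-width. A 3-letter bias at weight 1 gives 0.05 × 3 = 0.15 letters, or 0.15 / 2.3 = 6.5%.

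**4. Which earlier values carry the risk.** The SAP's imputation accounts for treatment group. A tester bias that is constant within an arm at the interim visits, and the same for completers and leavers, would be largely absorbed by that term. A bias confined to leavers, such as one arising at an unmasked closeout visit, would not be absorbed if that value enters. LOCF has no such term. For the primary analysis the table is therefore nearer an upper range than an expectation.

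**The case against.** The best case against the point has four parts.

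- **Stopping treatment is not withdrawal.** A reader might infer that anyone who stops injections or misses visits is lost to the endpoint. The documents do not support that. After an adverse effect of an injection, retreatment is left to the investigator; other DME treatment is possible with approval; a missed 12-week visit is foreseen (all in 4.8); and pregnancy stops study injections with no mention of leaving the study (4.8.6). Such eyes remain due at 24 weeks under 4.6. This part stands, and the point covers only people who leave the study. The protocol does not state the distinction, however.
- **Retention measures exist.** Section 5.7 has the principal investigator speak personally with anyone thinking of leaving and sets a goal of low loss. Section 5.9 plans a telephone contact before the 24-week visit. These should reduce the number affected, but neither asks someone who has already withdrawn to return for the endpoint.
- **The measurement may be sound.** A reader might infer that the imputation rests on unmasked data, with the closeout value as its dominant input. The text shows only that masking is not required. The participant is masked and acuity is tested electronically. The SAP does not say whether closeout counts as a follow-up visit, and section 4.6 does not list it. The point survives because weeks 4 to 20 also lack a tester-masking requirement.
- **The number is trivial.** Reading the loss as 75 − 70 = 5 eyes, all biased by 3 letters in one arm, gives 5/75 × 3 = 0.2 letters. The stated 5% supports about 4 eyes and 0.15 letters. LOCF is also not among the sensitivity analyses listed in the SAP, although the full analysis plan it refers to is not among the documents. The effect is indeed small.

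**Conclusion.** The point holds as a low-cost improvement, not as a threat to the primary conclusion. Followed as written, section 5.7 lets masked 24-week data go without asking for them, and the missing value is imputed from measurements that need not be masked. At the planned loss, about 4 eyes per group are involved, and the treatment difference would move by about 0.05 to 0.5 letters against a half-width of 2.3. That rests on an assumed between-arm bias of 2 to 10 letters, a weight of 0.5 to 1, and the bias being present in every imputed eye. The exposure matters more if loss is well above plan: at 15% the same assumptions give 0.15 to 1.5 letters. Two links rest on silence rather than on a stated rule: the timing of the closeout visit, and the absence of any request to return. The per-protocol analysis uses only eyes with 24-week data and is not exposed to the imputation.

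**What to change.** - **Protocol 5.7:** ask a participant who withdraws, with consent, to attend the 24-week visit for acuity and OCT. Hold a closeout visit at exit in addition, or as the fallback if the 24-week test is declined. State that stopping injections or missing interim visits is not withdrawal and that such eyes remain due at 24 weeks.
- **Protocol 1.4 and 4.7:** extend the masking of acuity testers, refractionists and OCT technicians to the closeout visit.
- **SAP item 4.b.i:** state whether a closeout value enters the imputation.

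Masking closeout leaves the values from weeks 4 to 20 as they are; the request for the 24-week test is what removes reliance on them. The cost is some scheduling effort, one line in the consent form and a visit payment for a few participants. The SAP names a database of September 2017, so for data already collected the practical step is to report, by arm, how many 24-week values were imputed and whether closeout values were used. The wording change would then serve the phase III trial that this study is meant to inform.
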